#### 7.8 SAFETY ANALYSIS

All safety analyses will be performed on the TS and displayed as randomised. Assignment of preferred terms to HLGT and SOC will be according to MedDRA "primary path".

#### 7.8.1 Adverse events

AEs will be coded using the most recent version of the Medical Dictionary for Regulatory Activities (MedDRA) at database lock.

The analyses of adverse events will primarily be descriptive in nature. All analyses of AEs will be based on the number of patients with AEs (and not on the number of AEs). The general AE analysis will include all AEs (including outcome events as reported by the investigator).

#### 7.8.1.1 Assignment of AEs to treatment

The analysis of AEs will be based on the concept of treatment-emergent adverse events (TEAE). That means that all AEs occurring between first study drug intake until 7 days after last permanent study drug stop will be considered as on-treatment, i.e. possible treatment interruption phases of a patient will be part of the on-treatment phase.

All AEs occurring prior to first study drug intake will be assigned to "screening". All AEs occurring after last study drug intake + 7 days will be assigned to "post-treatment", whereby the post-treatment phase according to the previous treatment will be used (post-Lina and post-Placebo respectively). AEs reported after the date of last contact + 1 day will be assigned to "post-study".

Patients who died before last drug intake + 7 days will have their on-treatment phase assigned until the date of death.

In addition to the primary treatment emergent approach displaying the on-treatment phase and post-treatment phase separately, all AEs after the first dose of study medication will be included in an additional analysis by treatment group.

Further additional approaches will be implemented for the presentation of adverse events:

• For cancer and pancreatic cancer in addition to the 'TEAE approach' on the treated set, all adverse events that occurred between first study drug intake up to study end will be presented.

There will be additional analyses including all patients who had a minimum cumulative study drug exposure of 6 months (excluding treatment gaps), using following two approaches:

- o considering all AEs starting from the date when 6 months cumulative exposure was reached up to last drug stop + 7 days
- o considering all AEs starting from date when 6 months cumulative exposure was reached up to individual day of trial completion
- For renal events, hepatic events, pancreatitis and skin lesions all adverse events that occurred between first study drug intake up until treatment stop + 30 days will be presented based on the treated set.
- Heart failure adverse events (based on narrow SMQ cardiac failure 20000004) will be analyzed following the 'TEAE approach' (all AEs occurring between first study drug intake until 7 days after last permanent study drug stop will be considered as ontreatment) and the concept where all AEs from first study drug intake up to study end are assigned to treatment.

For the subgroup analyses of adverse events (as specified in Section 6.4), all adverse events occurring between first drug intake until 7 days after last permanent treatment stop will be considered with the following exception: for subgroup analyses of pancreatic cancer all adverse events that occurred between first study drug intake until study end will be considered based on the treated set.

For these subgroup analyses, frequencies and incidence rates will be provided.

## 7.8.1.2 Intensity

Intensity is classed as mild/moderate/severe (increasing intensity). If a patient reports an AE more than once within that system organ class (SOC)/ Preferred term (PT), the AE with the worst case intensity will be used in the corresponding intensity summaries.

## 7.8.1.3 Relationship to trial medication

Relationship, as indicated by the Investigator, is classified as "not related" or "related". If a patient reports the same AE more than once within that SOC/ PT, the AE with the worst case relationship to trial medication will be used in the corresponding relationship summaries.

## 7.8.1.4 Analysis of other significant AEs

According to ICH E3 (4), AEs classified as 'other significant' will include those non-serious adverse events with:

- (i) 'action taken = discontinuation' or 'action taken = reduced', or
- (ii) marked haematological and other lab abnormalities or lead to significant concomitant therapy as identified by the Clinical Monitor/Investigator

The identification of category (ii) will be done by medical advisor based on the eCRF data prior to database lock.

#### 7.8.1.5 AE summaries

## 7.8.1.5.1 Frequency of patients with adverse events

No confirmatory analysis is planned for routine safety comparisons.

An overall summary of patients with TEAEs will be presented by treatment, including patients with any AE, severe AEs, investigator defined drug-related AEs, AEs leading to discontinuation of trial drug, serious AEs (SAEs), AEs leading to death, AEs of Special Interest (AESI) and other significant AEs.

Separate tables will be provided for patients with SAEs, for patients with drug-related AEs, for patients with AEs leading to treatment discontinuation, for patients with fatal AEs, for patients with AESI, and for patients with other significant adverse events. AEs will also be reported by intensity.

The frequency of patients with TEAEs will be summarized by treatment, primary SOC and PT. The SOCs will be sorted according to the standard sort order specified by the European Medicines Agency (EMA), preferred terms will be sorted by frequency (within SOC).

Frequency tables of patients with cancer (broad BIcMQ) by treatment, High level term (HLT) and preferred term will be provided.

For handling of missing or incomplete data refer to Section 6.6.

In addition, an analysis will be done on AEs and SAEs which are assigned to the following phases: screening, treatment, and post-treatment for each treatment group.

An overview of adverse events from patients screened, but not treated, will be included.

A table showing the frequency of patients with non-serious TEAE occurring with PT incidences > 5% within at least one treatment group will be presented by treatment and preferred term for disclosure on clinicaltrial.gov website. Additionally, the following analyses will be reported for disclosure on EudraCT:

- AEs per arm: This analysis includes the number of patients with serious AEs, patients with non-serious AEs >5%, as well as the total number of deaths (all causes), and the total number of deaths resulting from drug-related adverse events.
- Number of patients with serious AEs on preferred term level (grouped by standard SOC terms)

## 7.8.1.5.2 Adverse event incidence rates

In addition to the frequency tabulations, time-adjusted adverse event analyses will be performed by SOC and PT, or respectively HLT and PT for TEAEs, severe TEAEs, investigator defined drug-related TEAEs, other significant TEAEs, TEAEs leading to discontinuation of trial drug, serious TEAEs, TEAE leading to death and AESI and further events (defined in Section 7.8.1.11).

The time at risk in patient years is derived as follows:

#### Patients with AE:

time at risk (AE) [days] = start date of event with specified PT/SOC – treatment start date + 1

#### Patients without AE:

time at risk (AE) in days = end date of time at risk – study treatment start date + 1, where end date of time at risk is the minimum of date of last study drug intake + x days and date of death, if applicable.

The standard approach will be x=7 days, but for certain AEs in addition other approaches will be used.

Total AE-specific time at risk per treatment group is then derived as:

Time at risk (AE) [years] =

$$\frac{\text{Sum of time at risk [days] over all patients in a treatment group}}{365.25}$$

For 'each row of a table' (e.g. displaying an SOC), time at risk is calculated using start of first AE summarized in this row; e.g. for patient with AE in a specified SOC: Time at risk = start date of AE with specified PT in a SOC – treatment start date + 1.

The AE incidence rate per 100 patient years can then be calculated as follows:

Incidence rate [1/100 Patient years (pt-yrs)] =

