## 7.8.1.11 Further adverse events

Patients with the following adverse events will be tabulated by treatment group:

- arthralgia (defined by HLGT 'Joint disorders') (by HLT and PT)
- cancer (broad BIcMQ) (by HLT and PT)

For this 'AE concept' of arthralgia in addition frequency tables for serious adverse events and, adverse events leading to discontinuation from trial drug will be presented. The most recent version of the definitions of these AEs according to the respective most recent MedDRA version will be used. These will be stored in the CTMF.

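### Do the cancer and pancreatic-cancer incidence rates use a time at risk that does not match the period over which events are counted?

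*SAP*

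**What the plan says.** SAP 7.8.1.5.2 gives one written rule for time at risk. For a patient with the event, it runs from treatment start to the "start date of event with specified PT/SOC". For a patient without it, it also runs from treatment start, and the "end date of time at risk is the minimum of date of last study drug intake + x days and date of death". The sentence that follows reads: "The standard approach will be x=7 days, but for certain AEs in addition other approaches will be used". The adverse events meant and the approaches are not named there. The section covers the events of special interest, which include pancreatic cancer (SAP 7.8.1.6), and the further events of SAP 7.8.1.11, which include cancer.

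SAP 7.8.1.1 sets the event windows. For cancer and pancreatic cancer there are four:

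- the treatment-emergent window, to 7 days after the last permanent stop;
- first intake to study end;
- among patients with at least 6 months' cumulative exposure, from the date that exposure was reached to last stop + 7 days;
- in the same patients, "considering all AEs starting from date when 6 months cumulative exposure was reached up to individual day of trial completion".

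On subgroups the same section says that "for subgroup analyses of pancreatic cancer all adverse events that occurred between first study drug intake until study end will be considered", and then: "For these subgroup analyses, frequencies and incidence rates will be provided".

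**The concern.** A rate is interpretable only if numerator and denominator cover the same period. Protocol 3.3.4.1 keeps patients under observation after they stop drug, so off-drug time exists by design. If events are counted to study end while event-free patients are cut off at last dose + 7 days, the rate is too high. If events count only after 6 months' exposure while the clock starts at first dose, time in which no event could count enters the denominator and pulls the rate down. If the arms differ in how many patients stop drug, the error does not cancel in the comparison. Cancer and pancreatic cancer have dedicated safety analyses in this trial, so distorted rates would be noticed and quoted. A different value of x does not help: it still ties the end to last intake and leaves the start at first dose.

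**Working it through.** The plan states no cancer rate, person-years or discontinuation rate, so there is no figure of its own to reproduce. The check has two parts: setting windows against formula, and sizing what literal use would do.

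**Windows against the written formula**

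| Analysis (SAP 7.8.1.1) | Events counted | Fits the formula with x = 7? | Rate promised there? |
|---|---|---|---|
| Treatment-emergent | first intake to stop + 7 days | Yes | Yes, through 7.8.1.5.2 |
| Cancer, pancreatic cancer, overall | first intake to study end | No (end) | Says presented; no rate named |
| Pancreatic cancer, subgroups | first intake to study end | No (end) | Yes, explicitly |
| 6-month lag, first window | 6-month date to stop + 7 days | No (start) | Not named |
| 6-month lag, second window | 6-month date to trial completion | No (start and end) | Not named |

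The one firm gap is the pancreatic-cancer subgroup rate.

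**Size if the formula were applied literally to study-end events**

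Follow-up: 36 months' recruitment and 54 months' duration (Protocol 3.1) give 1.5 to 4.5 years under uniform accrual, mean 3.0. Assume a fraction q stops drug at a uniform time. Mean on-drug time is 3.0 × (1 − q/2), and 7 days is 7/365.25 = 0.019 years.

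- q = 0.20: on-drug 2.70 years; 3.0/2.719 − 1 = +10.3%
- q = 0.25: on-drug 2.625 years; 3.0/2.644 − 1 = +13.5%
- q = 0.35: on-drug 2.475 years; 3.0/2.494 − 1 = +20.3%

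If one arm had q = 0.20 and the other q = 0.25, the rate ratio would move by 2.70/2.625 = 1.029, about 3%.

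A simulation of 2,000,000 patients tests a harsher case: constant hazard of 1 per 100 patient-years, follow-up uniform on 1.5 to 4.5 years, permanent stopping at 10%, 20% or 30% per year, no deaths and no treatment gaps.

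| Rate per 100 patient-years | Matched denominator | Literal: 10% / 20% / 30% stopping per year |
|---|---|---|
| Treatment-emergent, x = 7 | 1.00 | same as matched |
| Events to study end | 1.00 | 1.17 / 1.39 / 1.65 |
| 6-month lag to stop + 7 days | 1.00 | 0.80 / 0.78 / 0.76 |
| 6-month lag to trial completion | 0.99–1.00 | 0.92 / 1.04 / 1.17 |

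Before rounding, the literal study-end rate exceeds the matched one by 17% to 64%. The lagged rate to stop + 7 days falls short by 19% to 24%. The lagged rate to trial completion goes from −7% to +17%, because the early start and the early stop pull in opposite directions. The simple model agrees. Ignoring the 7 days and the restriction to patients who reached 6 months, (3.0 − 0.5)/2.70 = 0.93, 2.5/2.625 = 0.95 and 2.5/2.475 = 1.01. So literal use does not always deflate the lagged rates.

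**Is literal use what the plan prescribes?**

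The x = 7 sentence calls that rule the standard and says other approaches will be added for certain adverse events. SAP 7.8.1.1 uses the same word, approaches, when it introduces the additional cancer windows. SAP 6.8 says that the time intervals of an analysis fix the start and end for deriving an event. SAP 6.8.3 defines the individual day of trial completion, and its x-day rules censor patients over the same window in which events count. Read together, these point to a denominator matched to the event window.

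**The case for a change.** The best case for a change rests on the pancreatic-cancer subgroups. A rate to study end is promised in plain terms, and the only denominator in view stops at last dose + x days. The reference to other approaches directly follows the value of x, so it could mean no more than other values of x, such as the 30-day window used for renal, hepatic, pancreatitis and skin events. Cases and non-cases are also treated unequally: a case's time runs to onset with no cap, while a non-case is cut at last dose + x days. A programmer working only from 7.8.1.5.2 could produce an inflated rate, and a sentence of text would prevent it.

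What stands is that no visible text states this denominator. That literal use is intended, or likely, does not stand. The plan says approaches, not values of x, and a statistician asked for a rate on events to study end would end time at risk at trial completion or death. The lagged half is weaker still, because 7.8.1.1 does not promise rates for those windows. The public text also has gaps at relevant points: the sentence on time-to-event analysis of adverse events in 6.8.1 breaks off, 6.8.3 refers to x-day rules that are not shown, and Table 6.7.2: 1 and Section 6.4 are not visible. The rule may be written there.

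**Conclusion.** This is a missing detail that analysts fill sensibly, and no change to the plan follows. The plan does not prescribe a wrong denominator for the extra cancer windows. It writes out the standard one, says other approaches will be used for certain events, and defines elsewhere the date needed to match a study-end window. The treatment-emergent rates for cancer and pancreatic cancer are consistent with the formula as written.

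The distortions calculated here (10% to 20%, or 17% to 64% under heavier stopping, for study-end rates; about 3% on the rate ratio for an assumed 5-point difference in stopping) would arise only from a literal reading, and they rest wholly on assumed discontinuation. The consequence is limited in any case. SAP 7.8.1.5.1 plans no confirmatory analysis of routine safety, and Protocol 7.3.3 keeps safety descriptive. Frequencies accompany the subgroup rates. Adjudicated pancreatic malignancy (SAP 7.8.1.8) and the oncology assessments (SAP 7.8.1.9) are tabulated to study end as frequencies, which need no person-time.

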# 7.8.1.6 Adverse events of special interest (AESI)

According to the protocol the following events are considered as AESI:

- Hypersensitivity reactions (defined by narrow SMQ 20000214 'hypersensitivity')
- Skin lesions (defined by narrow SMQ 20000020 'severe cutaneous adverse reactions')
- Hepatic events (defined by narrow sub-SMQ 20000010 'hepatitis, non-infectious',

narrow sub-SMQ 20000013 'hepatic failure, fibrosis and cirrhosis and other liver damage-related conditions', narrow sub-SMQ 20000008 'liver related investigations, signs and symptoms', narrow sub-SMQ 20000009 'cholestasis and jaundice of hepatic origin')

- Renal adverse (defined by narrow SMQ 20000003 'acute renal failure')
- Pancreatitis (defined by narrow SMQ 20000022 'acute pancreatitis' and PT 'Pancreatitis chronic' (resp. based on updated MedDRA version corresponding term for that )
- Thyroid neoplasm (benign) (BIcMQ Thyroid Neoplasms narrow BIcMQs, restricted to diagnoses (exclude symptoms) by TM DS (manual review))
- Thyroid cancer (presentation in table of cancer events by HLT and PT; and also under "Thyroid neoplasm" as defined above)
- Pancreatic cancer (based on narrow BIcMQ)

Patients with these AESIs will be tabulated by treatment group.

For all AESIs, in addition frequency tables for serious adverse events (except for thyroid neoplasm (benign), thyroid cancer, pancreatic cancer as always-serious events) and adverse events leading to discontinuation from trial drug will be presented.

The most recent version of the definitions of these AESIs at the time of the DBL will be used to be in line with the respective most recent AESI definition in the current MedDRA version. These will be stored in the CTMF.

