**Proprietary confidential information.**

© 2016 Boehringer Ingelheim International GmbH or one or more of its affiliated companies. All rights reserved.

This document may not - in full or in part - be passed on, reproduced, published or otherwise used without prior written permission.

- Renal adverse events such as acute renal failure
- Pancreatitis (refer to the ISF)
- Thyroid neoplasm (benign)
- Thyroid cancer
- Pancreatic cancer

~~A list of terms that must be documented as AESI for each topic is provided in the ISF. The renal events and pancreatic events will be adjudicated by independent adjudication committees.~~

~~AESI's, even though they might be non-serious are to be documented in the eCRF within 24 hours of receipt and must be reported to the sponsor/CRO in an expedited manner similar to Serious Adverse Events. For details please see [Section 5.2.2.2](#).~~

**Protocol-specified AESIs (as identified by the investigator based on the above definitions for adverse events of special interest) can be classified as serious or non-serious but all these AESIs once identified by the investigator must be reported on an SAE form in an expedited manner similar to SAEs, even if they do not meet any of the SAE seriousness criteria.**

**Beyond of this, and for the purposes of ongoing pharmacovigilance activities by the sponsor, adverse events based on additional searches for coded preferred terms of adverse events captured in the trial database (such as Special MedDRA Queries (SMQs), and user defined searches (BicMQs)) will be queried to verify with the investigator if the adverse event reported represent a suspected or diagnosed protocol specified AESI. AESIs once identified by the investigator must be reported on an SAE form in an expedited manner similar to SAEs, even if they do not meet any of the SAE seriousness criteria.**

**These additional searches (summarized under the so called 'overview of protocol defined AESIs and safety topics of interest') may change according to active pharmacovigilance of linagliptin. The most up to date list of these searches will be included in the ISF and changes will be communicated to all investigators.**

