**AEs considered "Always Serious"**

Proprietary confidential information.

© 2016 Boehringer Ingelheim International GmbH or one or more of its affiliated companies. All rights reserved.

This document may not - in full or in part - be passed on, reproduced, published or otherwise used without prior written permission.

**Cancers of new histology and exacerbations of existing cancer must be reported as a serious event regardless of the duration between discontinuation of the drug and the occurrence of the cancer. In accordance with the European Medicines Agency initiative on Important Medical Events, Boehringer Ingelheim has set up a list of further AEs, which by their nature, can always be considered to be “serious” even though they may not have met the criteria of an SAE as given above.**

**The latest list of “Always Serious AEs” can be found in the ISF. A copy of the latest list of “Always Serious AEs” will be provided to you upon request. These events should always be reported as SAEs as described above.**

BI has set up a list of AEs which are defined to be always serious. In order to support the investigator with the identification of these “always serious adverse events”, if a non-serious AE is identified to be serious per BI definition, a query will be raised. The investigator must verify the description and seriousness of the event. If the event description is correct, the item “serious” needs to be ticked and an SAE has to be reported in expedited fashion following the same procedure as above.

~~The list of these adverse events can be found in the ISF.~~

*For Japan: This information must be also reported immediately to the head of the trial site.*

With receipt of any further information to these events, a follow-up SAE report has to be provided. SAEs, **AESIs** and non-serious AEs must include a causal relationship assessment made by the investigator. The SAE form is to be forwarded to the defined unique entry point (contact details will be provided in the Investigator Site File). This immediate report is required irrespective of whether the investigational product has been administered or not and irrespective of causal relationship. It also applies if new information to existing SAEs or Adverse Events of Special Interest becomes available.

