**Proprietary confidential information.**

**© 2016 Boehringer Ingelheim International GmbH or one or more of its affiliated companies. All rights reserved.**

This document may not - in full or in part - be passed on, reproduced, published or otherwise used without prior written permission.

ethnicity), whether it is direct influence (e.g. due to hyperglycaemia), whether it is related to medical therapies used in the treatment of T2DM, or whether T2DM represents a condition with underlying biologic factors that alter cancer risk (e.g. insulin resistance and hyperinsulinemia) [R10-6496, R10-6498, R10-6536, R10-6497, R10-6494].

In order to assess patients with oncological adverse events (benign and malignant) in detail, and in addition to the AESIs thyroid neoplasm (benign), thyroid cancer, and pancreatic cancer, detailed information will be requested and should be provided by the site. The main focus on oncological adverse events is on the following organ systems, based on [R10-6638] where an increased risk for cancer in the population of patients with T2DM was described:

- Liver
- Endometrium
- Colon and rectum
- Breast
- Bladder
- Prostate

Request for detailed information (e.g. medical history, diagnostic result, laboratory results staging), will be mainly focused on the above listed organ systems, however is not restricted to them. **For details refer to the oncology committee assessment charter.**

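### SAP 7.8.1.6 counts thyroid cancers in the adverse-event-of-special-interest row labelled benign, so that row is really a combined row and no such row gives the benign count

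*SAP*

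**What the plan says.** Protocol 5.2.2.1 gives benign thyroid neoplasm and thyroid cancer separate entries in the AESI list. Protocol 5.2.2.3 keeps them apart again: "in addition to the AESIs thyroid neoplasm (benign), thyroid cancer, and pancreatic cancer".

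SAP 7.8.1.6 says that it follows the protocol's list and repeats both labels. Its definition of the benign item is "BIcMQ Thyroid Neoplasms narrow BIcMQs, restricted to diagnoses (exclude symptoms) by TM DS (manual review". Thyroid cancer has no query of its own; its entry reads "presentation in table of cancer events by HLT and PT; and also under", followed by a pointer back to the thyroid neoplasm entry. Pancreatic cancer, in the same list, does have its own narrow query.

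The same section plans AESI tables of serious events, "except for thyroid neoplasm (benign), thyroid cancer, pancreatic cancer as always-serious events".

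On seriousness, Protocol 5.2.2.2 states: "Cancers of new histology and exacerbations of existing cancer must be reported as a serious event". It then adds that "Boehringer Ingelheim has set up a list of further AEs, which by their nature, can always be considered to be" serious, and places the current list in the investigator site file. Protocol 5.2.2.1 says that the AESIs it specifies "can be classified as serious or non-serious but all these AESIs once identified by the investigator must be reported on an SAE form".

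**The concern.** The label and the content of one safety row disagree. If the row was meant to show benign neoplasms, its definition is too wide. If it was meant to show all thyroid neoplasms, its label is wrong. A programmer who follows the text will put malignant cases in a row that a reader of the trial report will take as benign, and the benign AESI named in the protocol will have no row of its own.

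The protocol describes AESIs as events of particular concern for safety monitoring, and says that the trial's data will support regulatory submission. Thyroid events are likely to be few, so a handful of misplaced cases could change how the row reads.

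A second, smaller question is why benign thyroid neoplasm is left out of the AESI serious-event tables, when nothing in the two documents names it as always serious.

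**Working it through.** The plan states no figure to reproduce on this point. The check is a comparison of texts, followed by a short piece of counting.

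**1. Are cancers really in the row labelled benign?** The contents of the company query are not in the documents, so its name alone would not settle this. Two parts of SAP 7.8.1.6 do. The only stated restriction is to diagnoses, with symptoms excluded; a malignant diagnosis is still a diagnosis. The thyroid cancer entry then says that cancers are shown under the thyroid neoplasm entry above, and only one entry fits that description. So they are in it.

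**2. What does the row count?** In one arm, let b be the patients with a benign thyroid neoplasm, c those with thyroid cancer, and o those with both.

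- Row as defined in the SAP: b + c − o
- Benign AESI as named in the protocol: b
- Excess: c − o, or (c − o)/b in relative terms

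The excess is zero only if every patient with thyroid cancer also has a benign neoplasm, which includes the case c = 0.

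**3. What happens to the incidence rate?** SAP 7.8.1.5.2 plans time-adjusted analyses for AESIs. A patient's time at risk ends at the first event summarised in that table row. Including cancers therefore raises the numerator by c − o. It also shortens time at risk for any patient whose cancer precedes a benign event or occurs without one.

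**4. Can the benign count be recovered elsewhere?** Not reliably. Subtracting the cancers requires o, which is not tabulated. It also mixes two searches, because the cancer table uses the broad cancer query and the thyroid row uses the narrow thyroid query. The general tables by system organ class and preferred term show single benign terms by arm. Adding those terms counts a patient with two of them twice.

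**5. Illustration, with assumed counts.** Suppose linagliptin has b = 10 and c = 6, and placebo has b = 12 and c = 1.

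| | Benign (b) | SAP row, o = 0 | Excess | SAP row, full overlap |
|---|---|---|---|---|
| Linagliptin | 10 | 10 + 6 = 16 | 6/10 = 60% | 10 |
| Placebo | 12 | 12 + 1 = 13 | 1/12 = 8% | 12 |

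With 3500 patients per arm and no overlap, the benign odds ratio is (10 × 3488)/(12 × 3490) = 0.83. The SAP row gives (16 × 3487)/(13 × 3484) = 1.23. The row labelled benign would then lean the other way from the benign events. These counts are invented to show the mechanism and say nothing about the trial.

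**6. Seriousness.** Protocol 5.2.2.2 makes cancers always serious and refers to a further list that is not reproduced. Protocol 5.2.2.1 says that AESI status alone does not settle seriousness. Neither document names benign thyroid neoplasm as always serious, and neither rules it out.

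**The case against.** The strongest reply is that the double presentation is stated openly. The pointer in the thyroid cancer entry drops the word benign, which suggests that a combined thyroid display was intended. Much of what a safety reader needs is also planned elsewhere. SAP 7.8.1.5.1 and 7.8.1.11 tabulate cancers by arm, high level term and preferred term. SAP 7.8.1.1 adds cancer analyses to study end and after six months' cumulative exposure, and SAP 7.8.1.9 describes an independent blinded committee that reviews suspected solid cancers. Adverse event analyses are primarily descriptive. All of this stands, and it makes the point minor. It does not make the label match the content.

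Four stronger readings are tempting, and the documents do not support them.

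- *That all thyroid AESI counts are wrong, or that thyroid cancer goes uncounted.* Only the row labelled benign is affected. Thyroid cancers can be read by arm in the cancer table.
- *That a cancer imbalance would be hidden.* In the illustration above, the 6 versus 1 cancers would still appear in the cancer table. The combined row would not replace them.
- *That only cancers are always serious, so the serious-table exception must go.* The protocol refers to a further always-serious list, and benign thyroid neoplasm may be on it. The documents cannot decide this.
- *That serious benign cases disappear.* The general serious adverse event tables still include them. Only the AESI-specific table is omitted, and that omission changes no AESI count.

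**Conclusion.** The point holds in a narrow form. As written, the row labelled benign combines benign and malignant thyroid diagnoses, contrary to the protocol's two separate AESIs, and no AESI row gives the benign count or rate. The excess in each arm is c − o patients; its value cannot be derived from the documents. The conclusion rests on reading the pointer in the thyroid cancer entry as referring to the only thyroid neoplasm entry above it.

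The always-serious status of benign thyroid neoplasm is unsupported in these documents but not contradicted by them. It calls for confirmation, not reversal.

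Both matters are minor and confined to descriptive safety tables. The primary and key secondary analyses are untouched.

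**What to change.** In SAP 7.8.1.6:

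1. Extend the manual review already planned for the Thyroid Neoplasms query, so that each diagnosis is classified as benign/unspecified or malignant. State that this is completed before unblinding; the SAP does not currently say that the review is blinded.
2. Define the benign AESI by the benign/unspecified cases and the thyroid cancer AESI by the malignant cases. Give each its own row with frequency and incidence rate.
3. If a combined row is wanted, label it *any thyroid neoplasm*. Relabelling alone would cure the mismatch but leave the benign AESI without a count.
4. Confirm, citing the list in the investigator site file, that benign thyroid neoplasm is always serious. If it is not on that list, produce its AESI serious-event table.

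The cost is a few lines of SAP text, one classification column in a review already planned, one or two table rows, and possibly one short table. No new data are needed.
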